3.3 Design Summary

This is a randomized control trial. Multiparous “low-risk” patients who meet inclusion criteria will be offered participation in the study. The intervention group will have a transcervical Foley catheter placed in the outpatient setting for cervical ripening after cephalic presentation is confirmed and the fetus has had a reassuring fetal heart rate tracing. The patients in the intervention group will then be sent home until a scheduled time to arrive the next morning to begin their induction of labor. The inpatient (control) group will undergo cervical ripening in the standard fashion with a transcervical Foley catheter while inpatient. Concurrent oxytocin administration with the transcervical catheter in situ will be at the discretion of the attending physician. Intervention (outpatient) group patients will be managed exactly the same as the control (inpatient) group once they are admitted. Thus, if the transcervical Foley catheter remains in situ when admitted, it can remain in place for up to 24 hours post-placement. Oxytocin may be started concurrently with the transcervical catheter in place, and amniotomy timing is at the discretion of the attending physician. The primary outcome is the time from admission to delivery between the two groups. Analysis will be on intent to treat basis.

3.4 Study Population and Eligibility Criteria

a. Inclusion criteria:

- i. Age ≥ 18
- ii. Multiparous
- iii. Singleton gestation
- iv. Gestational age between 39+0 and 42+0 weeks.
- v. Vertex presentation
- vi. Cervix ≤ 3 cm. If cervix is between 2 and 3 cm dilated, it must be $<80\%$ effaced
- vii. No prior cesarean section or uterine surgery
- viii. Resides within Jefferson County
- ix. Access to a telephone
- x. Reliable transportation

b. Exclusion criteria:

- i. Unsuitable for outpatient Foley placement management (IUGR, oligohydramnios, prior cesarean delivery, gestational hypertension, preeclampsia, uncontrolled chronic hypertension, complex maternal disease, provider discretion). Women with pregestational diabetes and those with gestational diabetes requiring medication will be excluded.
- ii. Latex allergy
- iii. Contraindication to induction of labor
- iv. Evidence of labor
- v. Fetal anomaly or demise
- vi. Inability to give consent (non-English, inability to read or write)

3.5 Gestational Age Determination

The gestational age will be already be determined prior to enrollment since all patients will be receiving care at the University of Alabama affiliated clinics. Per our Ultrasound Utilization in Obstetrics guideline, the ultrasound estimated due date (EDD) is based on the earliest ultrasound and not the stated last menstrual period (LMP) because of the inaccuracies and variability in menstrual cycles.

3.6 Study groups

There will be two intervention groups:

a. All patients:

- a. Patients will present to the 2nd floor of the CRWH for a scheduled OFFSITE study visit. This will occur every weekday except Friday.
- b. The order of events in the CRWH for all patients will be as follows:
 - i. Blood pressure evaluation
 - ii. Transabdominal ultrasound
 - iii. Vaginal examination
 - iv. Continuous fetal heart rate and tocometry monitoring for 20 minutes.
- c. If the patient's blood pressure is normal (<140 mmHg systolic and < 90 mmHg diastolic), ultrasound identifies a vertex fetus with normal amniotic fluid, cervix meets inclusion criteria (< 3 cm. If between 2-3 cm, then < 80% effaced), and the fetal heart rate tracing is category 1* without evidence of three contractions in a ten minute period, then the patient will be consented and randomized to either group 1 (standard treatment) or group 2 (intervention) and management will follow as detailed below.
 - i. Patients who do not meet cervical dilation criteria because of not needing cervical ripening (cervix >3 cm, or if 2-3 cm dilated and > 80%) will have their induction of labor canceled unless they are patients of the PrimeCare division.

b. Group 1 (Standard treatment)

- a. The patient will return the next day for her scheduled induction of labor at a pre-assigned time.
- b. Patient will be admitted to the labor and delivery floor and will be registered in the standard fashion by the nurse. The physician will be notified when the patient has had a reassuring fetal heart rate tracing and is ready for placement of the Foley catheter.
- c. The physician will perform an ultrasound to confirm vertex position and check the cervix. The patient will remain in the study even if she no longer meets cervical exam requirements (≤ 3 cm, if 2 cm, < 80% effaced) since the study design is intent to treat.

- d. Using the standard technique (dorsal lithotomy, betadine prep, sterile ring forceps, balloon inflated to 30 ml sterile saline), the transcervical Foley catheter will be placed transcervically. It is at the provider's discretion to tape this to the inner thigh or to leave it un-taped.
 - i. If the transcervical catheter is unable to be placed with a speculum and ring forceps, the provider may place with digital guidance.
- e. If the Foley catheter is unable to be placed secondary to the patient not being dilated enough to pass the catheter through the cervix, the patient will be asked to return in 24-72 hours later to again attempt placement of the Foley catheter. If the cervix is closed, there is a higher chance of a failed induction and cesarean section with proceeding with the induction of labor.
- f. As is standard in our practice, oxytocin will be initiated concurrently, and the fetal heart rate will be continuously monitored per protocol. The patient will remain NPO.
- g. A nurse or physician will assess the Foley bulb every 2-4 hours with gentle traction. It may be re-taped at this point.

c. Group 2 (Intervention)

- a. The transcervical Foley catheter will be placed in the exact manner as described in the above group 1 (standard treatment) description.
 - i. As the cervix effaces and dilates (aka ripens), it is normal to have a small amount of bleeding. Since this is a Foley catheter designed for use of draining urine from the bladder, the end of the catheter can drain a small amount of blood.
 - ii. If the Foley catheter is unable to be placed secondary to the patient not being dilated enough to pass the catheter through the cervix, the patient will be asked to return in 24-72 hours to again attempt placement of the Foley catheter. If the cervix is closed, there is a higher chance of a failed induction and cesarean section with proceeding with the induction of labor.
- b. The patient will undergo 30 more minutes of fetal monitoring and be discharged home if it is Category I. ‡
- c. The patient will then be given a sheet containing important information regarding reasons to present to the hospital prior to the scheduled induction the next morning. Importantly, the direct physician 24-hour triage line (MEU) will be clearly listed on the paper.
 - i. Reasons to return to the hospital or call the physician include:
 1. Standard labor precautions (decreased fetal movement, concern for rupture of membranes or contractions every 5 minutes for one hour)
 2. Uncontrolled pain, and/or vaginal bleeding soaking a pad or their underwear.

- ii. Patients will be instructed that a small amount of vaginal bleeding is to be expected as well as it is normal for the Foley catheter to be expelled as the cervix ripens.
 1. Thus, patients will be instructed to record the time of expulsion and report for their induction as scheduled unless any of the aforementioned conditions exist.
- iii. If a patient is admitted to the hospital prior to her scheduled induction time, she will remain in the study, and the time of admission will be recorded as the “admit” time.
- d. All women will have a time to arrive to the Women and Infants Center (WIC) for their scheduled induction.
- e. Upon admission to labor and delivery the next morning, the patients will undergo routine maternal and fetal assessment by the physician and nursing staff.
- f. The patient will be managed exactly the same as the inpatient (control) arm once admitted. Thus, if the Foley catheter is still firmly in place, it can remain for up to 24-hours post placement time. Similarly, oxytocin will be started upon admission. As in the control arm, timing of amniotomy is at the discretion of the attending physician.

* Should the initial fetal heart rate tracing not be a category 1 before the placement of the Foley catheter, the patient will be directly admitted to the labor room for induction of labor since she will be greater than 39 weeks. Since this is an intention-to-treat randomized controlled trial, the induction of labor will proceed as described in the “Inpatient Foley” arm of the study. The patient will be included in the outpatient group for the analysis.

‡ Should the fetal heart rate tracing not be a category 1 after placement of the Foley bulb or significant vaginal bleeding or rupture of membranes occurs, the patient will be directly admitted to the labor room for immediate evaluation. If stable to continue with induction of labor, the patient will be managed as described in the “Inpatient Foley” arm of the study. Outcomes will be analyzed in the outpatient group since this is an intention-to-treat analysis.

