1.2 Secondary Hypotheses

- a. Patients in the outpatient group will have higher satisfaction scores than those undergoing cervical ripening in the inpatient setting.
- b. The following hypotheses pertain to the incidence of the following events:
 - a. Outpatient cervical ripening will not increase the incidence of adverse outcomes compared to inpatient cervical ripening. Based on prior studies evaluating the safety of the transcervical Foley catheter, we do not anticipate there to be heavy vaginal bleeding, immediate need for delivery for a non-reassuring fetal heart tracing, or stillbirths in either group.
 - b. A small number of patients in the outpatient transcervical Foley catheter group will require admission prior to their scheduled arrival time because of intractable pain from the transcervical Foley catheter. Additionally, a small number of patients will require an epidural for pain control while the Foley catheter remains in situ.
 - c. Immediate delivery for non-reassuring fetal heart rate tracings after placement of the transcervical Foley catheter will not be required in either group.
 - d. A small number of patients in the outpatient transcervical Foley catheter group will present to the Maternity Evaluation Unit (MEU) for evaluation prior to their scheduled admission time.
 - e. Spontaneous rupture of membranes (SROM) will occur at similar rates in the two groups.
 - f. Outpatient cervical ripening with the Foley catheter will not increase infectious morbidity as compared to inpatient cervical ripening.
- c. Epidural usage, and thus immobilization, will be higher in the inpatient group compared to the outpatient group.
- d. The outpatient and inpatient groups will have similar rates of vaginal and cesarean deliveries.
- e. The following hypotheses pertain to oxytocin usage between the two groups:
 - a. The inpatient group will require longer duration of oxytocin infusion, higher cumulative doses, and higher maximum rates than the outpatient transcervical Foley catheter group.
- f. The outpatient group will have lower labor and delivery charges than the inpatient group.

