3.2 Secondary Research Aims

- a. To assess patient satisfaction in both groups of patients to determine if patients in the outpatient Foley catheter group have higher satisfaction rates compared to the standard inpatient induction method.
- b. To assess the incidence of adverse outcomes in both groups. This will be evaluated by vaginal bleeding greater than bloody show, intractable pain requiring early admission in the outpatient (intervention) group, intractable pain requiring epidural placement while the Foley bulb remains in situ, nonreassuring fetal heart rate tracings upon admission in the outpatient group, and nonreassuring fetal heart rate tracing prompting immediate delivery.
- c. To assess the incidence of the following:
 - a. Outpatient group presenting to the Maternity Evaluation Unit (MEU) prior to their scheduled admission time.
 - b. Outpatient group having spontaneous rupture of membranes (SROM) prior to their scheduled admission time.
 - c. Chorioamnionitis or endometritis in each group.
- d. To assess the total time of epidural use in each group.
- e. To compare the mode of delivery between the two groups.
- f. To assess the following oxytocin parameters between the two groups.
 - a. Total time of infusion.
 - b. Total cumulative dose of oxytocin infused.
 - c. Maximum rate (milliunits/min) of oxytocin infused.
- g. To compare labor and delivery charges between the two groups.
- h. To assess a composite neonatal outcome between the two groups based on the following parameters:
 - a. Apgar score < 7 at 5 minutes
 - b. Arterial cord blood gas pH < 7.1
 - c. Arterial cord blood gas base deficit > -12
 - d. Admission to the neonatal intensive care unit.

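### The protocol's list of reasons for outpatients to return or call names no sign of infection, although infection is one of its own safety outcomes

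*Combined protocol and SAP*

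**What the plan says.** In section 3.6, Group 2, item c, each outpatient goes home with an information sheet that carries a round-the-clock physician triage number. Item c.i describes its content. The lead-in is "Reasons to return to the hospital or call the physician include", and two entries follow:

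- c.i.1: "Standard labor precautions (decreased fetal movement, concern for rupture of membranes or contractions every 5 minutes for one hour"
- c.i.2: "Uncontrolled pain, and/or vaginal bleeding soaking a pad or their underwear"

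Item c.ii adds that slight bleeding is expected and that "it is normal for the Foley catheter to be expelled as the cervix ripens". Item c.ii.1 then tells women to note when the catheter came out and to "report for their induction as scheduled unless any of the aforementioned conditions exist".

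Infection is followed elsewhere in the protocol. Secondary hypothesis b.f in section 1.2 reads "Outpatient cervical ripening with the Foley catheter will not increase infectious morbidity as compared to inpatient cervical ripening". Aim c.c in section 3.2 is "Chorioamnionitis or endometritis in each group". Section 4.7, item f.b, makes chorioamnionitis diagnosed with the catheter still in place a serious adverse event. Section 4.8.2, item i, makes chorioamnionitis or endometritis a secondary outcome.

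**The concern.** A woman in the outpatient arm goes home, in most cases with a catheter through the cervix, and the protocol describes no scheduled contact with her until the next morning. Her return list is therefore the main means by which a problem at home reaches staff. The other adverse events that the trial follows and that she could notice herself (bleeding, pain, ruptured membranes) are on the list. Infection is not.

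What is at stake is patient safety only. An infection that begins at home without pain, heavy bleeding or suspected rupture of membranes could be recognised and treated later than it need be.

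**Working it through.** The point rests on reading the text; the only arithmetic bounds the size of the effect and the cost of the fix.

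**1. Count the reasons.** Item c.i.1 gives three and item c.i.2 gives two: 3 + 2 = 5. Infection signs among them (fever, chills, foul discharge): 0.

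**2. Compare the list with what the protocol follows.**

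| Event a woman could notice at home | Where the protocol follows it | On the return list? |
|---|---|---|
| Bleeding beyond show | 3.2 b | Yes |
| Intractable pain | 3.2 b; 4.8.2 c | Yes |
| Ruptured membranes | 3.2 c.b; 4.8.2 h | Yes |
| Infection | 1.2 b.f; 3.2 c.c; 4.7 f.b; 4.8.2 i | No |

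**3. Look for another route that fills the gap.** The ‡ note in 3.6 sends a woman straight to the labor room for a tracing that is not Category I, significant bleeding or ruptured membranes. Section 4.5 admits an outpatient who presents with pain. Neither mentions infection. The ordered checks at the study visit (3.6 a.b) are blood pressure, ultrasound, vaginal examination and fetal monitoring, with no temperature. The next planned assessment is on admission the following morning (3.6, Group 2, item e).

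**4. Compare with the control arm.** For inpatients the protocol says "A nurse or physician will assess the Foley bulb every 2-4 hours with gentle traction". That is not an infection check, so it shows only that staff are with these women at intervals while outpatients have no scheduled contact.

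**5. How long could a delay be?** The documents give no clock times. Assume placement between 08:00 and 17:00, the 30 minutes of monitoring in item b, and arrival between 06:00 and 08:00.

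- Shortest time at home: 17:30 to 06:00 = 12.5 h
- Longest time at home: 08:30 to 08:00 next day = 23.5 h

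This range is a ceiling on any delay. Reaching it would need fever from the moment of discharge, no listed symptom all night, and no call. A delay of some hours is the fair description.

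**6. Who is exposed?** At most the 64 planned outpatients, fewer after direct admissions. The figure of 64 in section 5.1 reproduces: for a difference of 12 h, SD 24 h, two-sided alpha 0.05 and 80% power, the t-test calculation gives 63.8 per group, rounded up to 64. Nothing in this point changes it.

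**7. What could the fix do to the primary outcome?** Under item c.iii an early admission starts the admission clock. If delivery time did not change, one early admission would lengthen that woman's interval by at most 12.5 to 23.5 h. The shift in the outpatient mean would be:

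- 12.5 / 64 = 0.195 h, and 0.195 / 12 = 1.6% of the target difference
- 23.5 / 64 = 0.367 h, and 0.367 / 12 = 3.1% of the target difference

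**The case against.** A reader might infer that the protocol tells a febrile woman to stay at home until her scheduled admission. The text does not support that. The only sentence about reporting as scheduled, c.ii.1, follows from the advice that expulsion is normal and addresses a woman whose catheter has come out. For a woman whose catheter is still in place, no sentence says to wait. The lead-in uses the word *include*, the list covers calling as well as returning, and a physician can be reached at any hour. This objection stands, and the point is limited accordingly. What remains is that a telephone number does not tell a woman that fever is a reason to use it, and that after expulsion the only stated exceptions are the five listed conditions.

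A reader might also infer that outpatients have no staff contact overnight. The documents support only that none is scheduled: calls and unscheduled visits are possible, and section 4.8.2, item g, counts early visits to the evaluation unit.

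The serious-event item in 4.7 f.b cannot be joined to c.ii.1 as one scenario. The first concerns a catheter still in place and the second an expelled one. Item f.b shows only that the protocol regards infection as serious.

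Section 4.7 states that the catheter does not raise the risk of chorioamnionitis, and the women are selected as low-risk. That bears on how often infection occurs, not on whether a case at home is recognised.

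The strongest reservation is that the sheet the patient actually reads is not among the documents. It may already name fever, in which case no patient is affected and only the protocol text needs the line.

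**Conclusion.** The point holds as a minor, inexpensive improvement to patient safety. None of the five listed reasons is an infection sign, no other part of the protocol supplies one for the time at home, and the protocol itself treats infection as a hypothesis, an aim, a serious event and an outcome. Recognition could be delayed by some hours. The 12.5 to 23.5 h ceiling rests wholly on assumed clock times. The documents give no infection rate, so no number of late cases is claimed.

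The gap leaves the primary outcome and the sample size unaffected. The chorioamnionitis or endometritis comparison is taken from charts and does not require the catheter to be in place, so it is little affected. Confidence is medium because the patient sheet is unseen.

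**What to change.** Add fever (with a temperature threshold set by the clinical leads), chills and foul discharge to the reasons in section 3.6, Group 2, item c.i. The exceptions in c.ii.1 refer back to that list and would then cover them without further change. Make sure the patient sheet carries the same list; if it already does, only the protocol needs the line.

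The cost is one line of text and IRB approval of the wording. The downside is a few more calls or early visits; the visits are already captured as outcome g. Any resulting early admission has at most the small effect on the outpatient mean shown above.

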4.1 Screening for Eligibility and Consent

All patients will be identified utilizing the IRB-approved UAB Obstetric Automated Recording (OBAR) system (IRB X030604010). This system will be used to identify patients entering the 37th-42nd week of pregnancy. Those initially meeting eligibility criteria by chart review will be called via the “phone script” (see phone script attached). If the patient continues to meet eligibility criteria after completing the “phone script,” she will be scheduled in the UAB Obstetrics Complications Clinic (OBCC) for her next appointment (between 37th-42nd weeks of gestation) where a co-investigator will present the study which will include the risks, benefits, procedures, and alternatives. The informed consent will be signed after all questions have been answered. The induction of labor will not be conducted prior to 39+0 weeks’ gestation.

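### A footnote in 3.6 assigns women who fail the entry tracing to the outpatient group for analysis, although on the 3.6 sequence they have not been randomized

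*Combined protocol and SAP*

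**What the plan says.** All of the following is in the combined protocol and SAP.

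- **3.6, part a (all patients), item c.** Among the conditions to be met at the study visit is that "the fetal heart rate tracing is category 1* without evidence of three contractions in a ten minute period". If all are met, "then the patient will be consented and randomized to either group 1 (standard treatment) or group 2 (intervention". The asterisk sits on a condition that comes before allocation and applies to every patient.
- **3.6, footnote \*.** The trigger is "Should the initial fetal heart rate tracing not be a category 1 before the placement of the Foley catheter". The woman is then admitted directly, and "Since this is an intention-to-treat randomized controlled trial, the induction of labor will proceed as described in the" inpatient arm. The footnote ends: "The patient will be included in the outpatient group for the analysis".
- **3.6, footnote ‡.** This covers problems after catheter placement and hangs on a Group 2 step. Its rule is "Outcomes will be analyzed in the outpatient group since this is an intention-to-treat analysis".
- **3.3.** The intervention group's catheter is placed "for cervical ripening after cephalic presentation is confirmed and the fetus has had a reassuring fetal heart rate tracing".
- **4.1.** Consent is taken at an earlier clinic appointment: "The informed consent will be signed after all questions have been answered".
- **4.2.** Randomization follows confirmation of eligibility and consent. The tracing is not mentioned, and it is not among the criteria in 3.4.

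**The concern.** Intention to treat means analysing each randomized woman in the group to which she was allocated. It says nothing about a woman who was never allocated. Taken with 3.6 item c, footnote \* puts such women in the outpatient group and has no counterpart for the inpatient group.

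Followed as written, the rule adds to one arm women who were not randomized and who were selected because their tracing was not Category 1. They would enter the primary comparison of admission-to-delivery time, where the bias could go either way. They would also enter comparisons plausibly related to the selection, such as mode of delivery and the neonatal composite. Section 5.2 already concedes limited power for small differences in most secondary outcomes, so a few selected women in one arm could matter where counts are low.

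**Working it through.** **1. Which women does the footnote cover?**

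| Place | Order it implies | Does the woman have an allocation? |
|---|---|---|
| 3.6 item c | tracing, then consent, then randomization | No, if she fails the tracing |
| Footnote \* | before catheter placement; no allocation condition | Not stated |
| Footnote ‡ | after placement in Group 2 | Yes, outpatient |
| 3.3 | tracing before placement in the intervention group | Suggests yes, but does not state when randomization occurs |
| 4.1 and 4.2 | consent at an earlier visit; randomization after eligibility and consent | Either order is possible |

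Only 3.6 item c orders the tracing against randomization, and it puts the tracing first. Footnote ‡ is sound because its women are already allocated. Footnote \* has no such basis.

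**2. The plan's own sample size.** Inputs from 5.1 and 5.3: two-sided t-test, alpha 0.05, SD 24 h, difference 12 h, 80% power. The standardized difference is 12/24 = 0.5. The two-sample t calculation gives 63.8, rounded up to 64 per group, with power 80.1%. The plan's figure is reproduced.

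**3. Effect of the rule as written.** Let k women be added to the 64 randomized outpatient women, and let f be the hours by which they deliver faster than the control mean.

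- Expected difference = (12 × 64 + f × k)/(64 + k)
- Power: two-sample t, groups of 64 and 64 + k, SD 24 h

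With f = 0 (times like control):

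| k | Difference (h) | Power |
|---|---|---|
| 0 | 12.00 | 80.1% |
| 1 | 768/65 = 11.82 | 79.2% |
| 2 | 768/66 = 11.64 | 78.3% |
| 3 | 768/67 = 11.46 | 77.4% |
| 5 | 768/69 = 11.13 | 75.6% |
| 6 | 768/70 = 10.97 | 74.7% |

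Each added woman costs about 0.18 h and 0.9 points of power. It takes 6 to bring power below 75%, which is 6/134 = 4.5% of the women reaching the tracing.

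**4. By failure rate.** The documents give no rate, so s is assumed. With 128 women randomized, k = 128 × s/(1 − s).

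| s (assumed) | k | Difference, f = 0 | Power, f = 0 | Difference, f = 24 h (assumed) |
|---|---|---|---|---|
| 1% | 1.29 | 11.76 h | 79.0% | 12.24 h |
| 2% | 2.61 | 11.53 h | 77.8% | 12.47 h |
| 5% (illustration only) | 6.74 | 10.86 h | 74.0% | 13.14 h |

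The last column shows that the bias can also favour outpatient. Under no true effect, f = 24 h would raise the type I error from 5% to about 5.1% at s = 1% and 5.6% at s = 2%.

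**5. The other reading.** Suppose a fraction s of the 64 women allocated to outpatient fail the tracing and have control-like times. The difference is then 12 × (1 − s): 11.88 h and 79.4% power at 1%, 11.76 h and 78.5% at 2%, 11.40 h and 76.0% at 5%. This is ordinary intention-to-treat dilution, not bias, and the correction below does not alter it.

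**The case against.** The strongest reply is that footnote \* was written for women already allocated to outpatient. At the study visit only Group 2 receives a catheter, so a reference to the time before placement fits that group. The footnote contrasts her care with the inpatient arm, and it appeals to intention to treat, which presupposes an allocation. Footnote ‡ is its parallel, 3.3 describes the tracing within the intervention procedure, and 3.4 lists no tracing criterion. Section 3.7 also requires consent before enrolment, so on the strict 3.6 order a woman who fails would be unconsented as well as unrandomized and could not properly be analysed.

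This reading is plausible, and on it analysis in the outpatient group is correct. It does not clear the text. No section puts randomization before this tracing. The 3.7 point is a further conflict with the footnote, not a resolution of it. And if randomization did come first, the footnote still lacks an allocation condition although it hangs on an all-patients step, so a woman allocated to inpatient who failed the tracing would be analysed in the wrong arm.

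Two narrower points stand. The effect on the primary result is small at plausible rates, and the 24 h scenario has no anchor because the plan gives no control mean. The effect on secondary outcomes is not quantified and is limited for the tracing outcomes in 4.8.2: tracing on admission is recorded only for outpatients, so there is no between-group comparison to bias, and the immediate-delivery outcome requires the catheter to be in place, so the triggering tracing is not itself an event.

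**Conclusion.** The concern holds. As written, footnote \* places women without an allocation in the outpatient group and wrongly calls this intention to treat. The case rests on the integrity of the randomized comparison, not on a large loss of power. At an assumed 1–2% failure rate the primary difference moves by about half an hour or less in either direction, and with control-like times power drops by one to two points. A material loss would need a rate near 4.5% or more. If the authors meant only women already allocated to outpatient, there is no bias and the wording alone is at fault. It should be corrected. Confidence is medium, because the intended order of events cannot be settled from the documents.

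**What to change.** 1. State one order of consent, tracing and randomization, and make 3.3, 3.6, 4.1 and 4.2 agree with it.
2. Replace the last sentence of footnote \* with: *Only randomized women are analysed, each in her allocated group; a woman whose tracing is not Category 1 before randomization is recorded as a screen failure and is in neither group.*
3. Remove the appeal to intention to treat as the reason for her care, and leave the clinical pathway as it is.

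The replacement sentence works under either order. If randomization comes first, the screen-failure clause applies to nobody, and women allocated to outpatient stay in that group.

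The footnote costs only wording. Settling the order may change when consent and randomization are done around the study visit. Screen failures are reported in the participant flow and do not count toward the 64 per group, so the sample size and its 80.1% power are unchanged.
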